5.3.1.2.2. Supplementary Estimands

The supplementary estimands defined below will be used for the pairwise comparisons of the analyses specified in Section 5.3.1.2.3.1.

5.3.1.2.2.1. Supplementary Estimand 1 (Hypothetical Estimand):

In this supplementary estimand, the only component that changes from the definition of the primary estimand is the hypothetical strategy will be used for addressing ICEs 1-3.

Hypothetical strategy: assess the treatment effect as if the intercurrent event would not have occurred. Under the hypothetical strategy, data collected after ICEs 1-3 will not be used in analysis and will be imputed using a MAR multiple imputation method.

5.3.1.2.2.2. Supplementary Estimand 2 (Treatment Policy Estimand):

This supplementary estimand has the same components as the primary estimand, except for the strategies used for ICEs 1-3.

Treatment policy strategy: assess the treatment effect regardless of whether or not intercurrent events had occurred. Under the treatment policy strategy, observed data collected after ICEs will be used in analysis.

5.3.1.2.3. Analysis Methods for the Primary Estimand

The primary endpoint will be analyzed based on the primary estimand (Section 5.3.1.2.1) and the data from all participants in FAS (Section 4.1) will include data from all randomized participants who received at least one administration of study intervention based on their assigned intervention group, regardless of the actual intervention received.

Participants with ICEs 1-2 before Week 16 will be considered as PASI75 non-responders at Week 16. Participants with ICE 3, observed PASI data after this ICE will be utilized in the analysis. After accounting for the ICEs for the primary estimand, participants with the missing data of the primary endpoint at Week 16 will be considered as non-responders.

The MCP-Mod will be used to test if there is a positive overall treatment effect based on candidate dose-response models. For each candidate model a contrast test statistic, based on a linear combination of the treatment estimates per dose will be derived. The contrast coefficients will be chosen to maximize the power to detect the pre-specified candidate models. The global test decision is based on the maximum of the contrast test statistics. The overall positive dose-response will be tested at a 2-sided 5% significance level. This procedure takes into account the multiplicity arising from testing several models and thus preserving the family wise Type I error rate.

CCI

Generalized Multiple Comparison Modelling (gMCP-Mod)

To demonstrate the dose-response relationship across JNJ-77242113 treatment groups and placebo for the primary endpoint, the primary analysis will be based on a generalized Multiple Comparisons and Modeling (gMCP-Mod) analysis^{1,2}. This analysis tests for a dose-response relationship, allowing for uncertainty in the dose-response relationship through inclusion of contrasts from multiple pre-specified candidate models to assess dose-response. If a dose-response relationship exists, then fitted estimates for the incidence of the primary endpoint will be calculated in each of the treatment groups using the selected dose-response models.

The gMCP-Mod procedure extends the MCP-Mod methodology to non-continuous endpoints. This is accomplished by decoupling the dose-response model from the expected response through the use of an ANOVA style parameterization of the dose-response parameter. For the binary endpoint used in this study, a logistic regression of the event proportion at each dose level will be used. After this first step, the mean parameter estimates from the logistic model and the corresponding covariance matrix, both of which are on the logit scale, will then be used during the rest of the gMCP-Mod procedure. Point estimates from the selected models will be displayed on the proportion scale in all statistical outputs.

Candidate Models and Multiple Testing Procedure

There are six candidate models (Section 3.1) that will be considered for the primary analysis. These are 2 Emax models ($ED_{50} = 35$ mg and 50 mg respectively), logistic model ($ED_{50} = 35$ mg, $\delta=15$), SigEMax model ($ED_{50} = 35$ mg, $h=3$), linear model, and quadratic model ($\delta=-0.002$) where dose-response will be tested using dose levels of 0 (placebo), and JNJ-77242113 treatment groups⁴.

The gMCP-Mod procedure requires certain parameter estimates be pre-specified for the candidate models based on available information in order to derive optimum contrast coefficients for testing the null hypothesis: that a dose-response does not exist in any of the candidate models. It is through testing this hypothesis that the model which best describes the dose-response relationship will be identified. The parameters used to determine the contrast for testing will assume a placebo PASI 75 rate of 6% and maximum treatment effect be 74% (placebo-adjusted).

The gMCP-Mod procedure for non-continuous endpoints diverges from the original MCP-Mod procedure in the calculation of the optimum contrast coefficients. The gMCP-Mod methods that will be used to calculate the optimum contrast coefficients require the pre-specified model parameters from above along with the covariance matrix from the logistic regression in the first step. In practice, since the covariance matrix in the first step is based on actual data, the optimum contrast coefficients are recalculated when the actual data become available. The parameter estimates for the candidate models, however, will remain fixed.

For each candidate model, the contrast test statistic (z_m) is calculated as standardized linear combinations of the estimated event rate on the logit scale from the logistic regression using the optimal contrast coefficients associated with that candidate model. The optimal contrast coefficients are listed in [Table 5](#)

A multiplicity-adjusted critical value will be determined from the joint multivariate normal distribution of the contrast test statistics at the overall one-sided alpha level of 0.025. If at least one of the test statistics exceeds this critical value, a dose-response relationship is demonstrated.

CCI

[figure not shown]

Table 5: Optimal contrast coefficients for each candidate response curve

Candidate models/Doses	0 mg	25 mg	50 mg	75 mg*	100 mg	300 mg**
EMax1 (ED ₅₀ =35)	-0.6154	-0.294	-0.0982	0.0773	0.2572	0.6731
Emax 2 (ED ₅₀ =50)	-0.5451	-0.3132	-0.1366	0.0382	0.2263	0.7304
Logistic (ED ₅₀ =35, $\delta=15$)	-0.5557	-0.4825	-0.0921	0.2487	0.4277	0.453
SigEMax (ED ₅₀ =35, $h=3$)	-0.5656	-0.497	-0.0344	0.2295	0.3942	0.4732
Linear	-0.2081	-0.2206	-0.2132	-0.1741	-0.0917	0.9077
Quadratic ($\delta=-0.002$)	-0.3778	-0.3314	-0.2289	-0.0578	0.1849	0.8109

* 25 mg BID

** 100 mg BID.

Modelling and Estimation

The model for estimation will be selected from among the six candidate models with a contrast test statistic that is greater than or equal to the multiplicity-adjusted critical value. If 2 or more candidate models have such contrast test statistics, then these models will be employed using a weighted averaging technique based on their relative Akaike Information Criterion (AIC), for the purposes of estimation. If no candidate model has a contrast test statistic that is greater than or equal to the multiplicity-adjusted critical value, then the analysis will end, indicating that a dose-response relationship cannot be established.

5.3.1.2.3.1. Pairwise Comparisons

In addition to the dose-response analysis, pairwise comparisons of each JNJ-77242113 treatment group versus the placebo group will be performed for the primary endpoint of PASI 75 at Week 16. Pairwise comparisons will not be adjusted for multiplicity. The Cochran-Mantel-Haenszel chi-square statistic stratified by baseline weight category (≤ 90 kg, > 90 kg) at a 2-sided significance level of 0.05 will be used. Difference in response rates between each of the active groups and the placebo group adjusted for baseline weight category (≤ 90 kg, > 90 kg) using Mantel-Haenszel weight and the corresponding 95% CI will be presented.

In addition, the proportion of participants achieving a PASI75 response at Week 16 by investigator site will be summarized.

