A unified strategy that combines MCP-Mod techniques, will be used to analyze the dose-response relationship for the JNJ-77242113 doses in PASI 75 at Week 16. This approach consists of 2 major steps. The first step consists of testing the dose-response signal via multiple contrast tests while controlling the overall Type 1 error. If a dose-response signal is detected, the second step is to select a model that best describes the observed data, which may be used to support dose selection in future studies. In addition, a simple semi-parametric Bayesian normal dynamic linear model (NDLM) will also be explored to complement the frequentist MCP-Mod analysis. The details of the dose-response analysis will be provided in the SAP.

The study will be considered positive if a dose-response signal for the primary endpoint is detected. In addition to the dose-response analysis, pairwise comparisons of the JNJ-77242113 groups versus the placebo group will be performed for PASI 75 at Week 16; these comparisons will not be adjusted for multiplicity. For these comparisons, a CMH stratified by baseline weight category ($\leq 90\text{kg}$, $>90\text{kg}$) will be used. The proportion difference between each JNJ-77242113 group and placebo group and its 2-sided 95% CI will be provided based on normal approximation with Mantel-Haenszel weights adjusting for baseline weight category.

To examine the robustness of the primary endpoint analysis, additional analyses will be conducted using different missing data approaches; these analyses will be described in the SAP. In addition, sensitivity analyses will be performed for the primary endpoint using the per-protocol population, which includes participants who are generally compliant with the protocol. To evaluate the consistency of the efficacy, subgroup analyses of the primary endpoint will be performed.

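### The visible SAP text gives no zero-responder rule for the primary gMCP-Mod analysis; with an ordinary logistic fit, 0/40 on placebo removes placebo from the test and can lose the signal when active arms are close together

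*SAP*

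**What the plan says.** The first step of the primary analysis in SAP 5.3.1.2.3 is described as follows: "a logistic regression of the event proportion at each dose level will be used". Its logit estimates and their covariance matrix "will then be used during the rest of the gMCP-Mod procedure". Because the contrasts depend on that covariance, "the optimum contrast coefficients are recalculated when the actual data become available"; only the candidate-model parameters stay fixed. The test statistic is then defined, followed by a cross-reference: "The optimal contrast coefficients are listed in" Table 5. A candidate model counts as significant if its statistic reaches a multiplicity-adjusted critical value at one-sided 0.025. If none does, "then the analysis will end, indicating that a dose-response relationship cannot be established".

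Protocol 9.4.2.1.1.1 makes this the only success criterion: "The study will be considered positive if a dose-response signal for the primary endpoint is detected". The selected model is one "which may be used to support dose selection in future studies", and the SAP promises that "fitted estimates for the incidence of the primary endpoint will be calculated in each of the treatment groups".

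The visible text has no penalisation, continuity correction or other rule for an arm with no responders. The one rare-event rule, Fisher's exact test, is in SAP 5.4.1.3.1 under the secondary binary endpoints. It covers treatment comparisons and cannot supply logits and a covariance to gMCP-Mod.

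**The concern.** With one parameter per arm, the maximum-likelihood logit for an arm with 0/40 responders is minus infinity and its variance is unbounded. Software returns whatever it had when it stopped iterating. Since every later step uses that covariance, the arm is in effect discarded. When the arm is placebo, the test that defines a positive study no longer uses the placebo comparison.

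The direction is perverse. Going from one placebo responder to none is stronger evidence for the drug, yet it can turn the study negative. If no rule is written down, a repair would be chosen after the placebo count is known. Missing Week 16 data count as non-response under SAP 5.3.1.2.3, which makes an empty placebo arm somewhat more likely.

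**Working it through.** **Inputs.** From SAP 3.1 and 5.3.1.2.3: n = 40 per arm; placebo rate 6% and maximum effect 74 points, so 80% at the top; placebo range 5% to 10%; six candidate models; Table 5 dose axis 0/25/50/75/100/300; one-sided 0.025. Assumptions of mine: no covariates in the logistic model, and an unpenalised fit.

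**Reproducing the plan.** The optimal contrast is c_i ∝ w_i(μ_i − μ̄_w), with w_i = 1/v_i, μ the candidate curve on the logit scale and μ̄_w its w-weighted mean. With v taken from the linear candidate's rates at n = 40, all of Table 5 reproduces to within 0.001. The largest gap is the logistic model at 50 mg: −0.0912 computed, −0.0921 printed. Power by the multivariate normal calculation is above 99.9% for every candidate, consistent with the >95% in Table 2.

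**Chance of an empty placebo arm.**
- 6%: 0.94^40 = 8.4%
- 5%: 0.95^40 = 12.9%
- 10%: 0.90^40 = 1.5%

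**What 0/40 does.** For r responders, v = 1/r + 1/(40 − r). At r = 1, v = 1 + 1/39 = 1.03. At r = 0, v is unbounded; a standard GLM fit stopped at logit −23.6 with SE 12,564. So w_0 goes to 0, and the recalculated placebo coefficient is of order 10^-9 or smaller in all six contrasts.

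**Worked example, recalculated contrasts, active counts 22/24/26/28/28 of 40.**
- Placebo 1/40, ordinary fit: maximum z = 3.51, critical value about 2.26; positive.
- Placebo 0/40, ordinary fit: maximum z = 1.62, critical value about 2.24; negative.
- Placebo 0/40, Firth: logit ln(0.5/40.5) = −4.39, variance 1/0.5 + 1/40.5 = 2.02; maximum z = 2.81, critical value about 2.26; positive.

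**Power given 0/40, ordinary fit, recalculated contrasts (simulation).**
- Six candidate curves: at least 99.7% with an 80% top rate and at least 98% with the protocol's 70%.
- Actives 40/47.5/55/62.5/70%: about 82%.
- Actives 45/52/58/64/70%: about 66%.
- Actives 55/60/65/70/70%: about 35%.
- All actives 70%: about 2%.

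The last four profiles are mine and are not in the SAP. Simulation error and the exact critical value move these figures by a point or two.

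**Overall loss at a 6% placebo rate.** Overall power in the last two profiles is about 93% and 81%. The points lost to 0/40 are 8.42% × (1 − 0.35) = 5.5 and 8.42% × (1 − 0.02) = 8.2. A sparse but non-empty placebo arm (1 to 3 responders) costs a further 1.6 and 10.9 points.

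**The case against.** **The planned power is untouched.** This stands. On all six candidates the active arms alone carry enough trend, and the losses need flatter profiles that the documents do not posit. In the flattest one, a sparse non-empty placebo costs more (10.9 points) than an empty one (8.2), so part of the problem is the logit variance and the candidate shapes, not the missing rule. Even so, a plateau across active doses is an ordinary dose-ranging outcome, and a stated rule should not reward an extra placebo responder.

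**Redaction.** Blacked-out text lies within this section and may already contain a rule. The point is therefore limited to the visible text.

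**Other analyses survive 0/40.** The stratified CMH comparisons (SAP 5.3.1.2.3.1) still work, and the Bayesian sensitivity model (SAP 5.3.1.2.4) puts a prior on placebo. Neither defines success, and the Bayesian model is for internal use only.

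**A stronger reading of Table 5.** A reader might infer from the cross-reference that the printed coefficients decide the test. An ordinary fit with 0/40 would then give z of about 0 on every candidate, and overall power would be about 88 to 92%, below Table 2. The documents do not support this. The SAP says the coefficients are recalculated from the observed covariance, and Table 5 matches a planning covariance. What remains is a loose cross-reference without a planning label.

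**Conclusion.** The point holds for the visible text and should be fixed before unblinding. If the first step is an unpenalised fit and the contrasts are recalculated as the SAP states, an empty placebo arm makes the primary test blind to placebo and can produce a negative study from data that favour the drug.

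The 8.4% is the probability of an empty placebo arm at 6%, not of a failed trial. It would be wrong to infer that Table 2 is overstated: power on the candidate curves stays near 100%. The material losses (power given 0/40 of about 82%, 66%, 35% and 2%) rest on my assumed active profiles. The same covariance also enters the model fits, so the fitted placebo rate could be affected too. I put no figure on that, because the visible text does not give the fitting algorithm. Confidence is medium, mainly because of the redactions.

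**What to change.** Unless the redacted text already does so, add to SAP 5.3.1.2.3 before unblinding:

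1. The first-step logistic model is fitted with Firth's penalised likelihood (with one parameter per arm, this adds 0.5 to responders and 0.5 to non-responders in each arm), and its estimates and covariance are used throughout gMCP-Mod.
2. Table 5 shows planning values; the decision uses the recalculated contrasts.

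The cost is two sentences, with no change to data collection. Estimates shrink slightly: for 2/22/24/26/28/28 the maximum z moves from 4.26 to 4.47. In simulation Firth does not inflate type I error but stays conservative at low null rates. At common rates of 5, 6 and 10%, one-sided error is 0.6, 0.7 and 1.0% with Firth, against 0.5, 0.7 and 1.0% with the ordinary fit; at null rates of 20 to 50%, Firth gives 1.4 to 2.1%.

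The repair is incomplete. Firth with recalculated contrasts keeps about 100% power given 0/40 on the candidates, but only about 70 to 75% at 55/60/65/70/70% and just under 20% with all active arms at 70%.

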6.3. Measures to Minimize Bias: Randomization and Blinding

Intervention Allocation

Procedures for Randomization and Stratification

Dynamic central randomization will be implemented in conducting this study. Participants will be assigned to 1 of 6 intervention groups based on an algorithm implemented in the interactive web response system (IWRS) before the study. Dynamic central randomization minimizes the imbalance in the distribution of the number of participants across intervention groups within the levels of each individual stratification factor: study site and baseline weight (≤ 90 kg, > 90 kg). In addition, the Japanese sites will be pooled in the randomization process to better ensure treatment balance across Japanese participants. Based on the algorithm, the IWRS will assign a unique intervention code, which will dictate the intervention assignment and matching study intervention kit for the participant.

Blinding

The investigator will not be provided with randomization codes. The codes will be maintained within the interactive web response system (IWRS), which has the functionality to allow the investigator to break the blind for an individual participant.

Data that may potentially unblind the intervention assignment (ie, study intervention plasma concentrations, anti-JNJ-77242113 antibodies, study intervention preparation/accountability data, intervention allocation, and biomarker data) will be handled with special care to ensure that the integrity of the blind is maintained and the potential for bias is minimized. This can include making special provisions, such as segregating the data in question from view by the investigators, clinical team, or others as appropriate until the time of database lock and unblinding.

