3. SAMPLE SIZE DETERMINATION

3.1. 77242113PSO2001

This study is designed to enroll approximately 240 participants, in order to provide sufficient data to have adequate power to detect a JNJ-77242113 dose-response signal for the proportion of participants achieving PASI 75 at Week 16 using the Multiple Comparison Procedures with modeling techniques (MCP-Mod) method.

The sample size of 240 participants was also chosen in order to have sufficient power to detect a difference between the JNJ-77242113 groups and the placebo group for the primary endpoint of the proportion of participants achieving PASI 75 at Week 16.

The assumptions for the sample size and power calculations specified below were mainly based on the clinical data from the guselkumab Phase 2 and Phase 3 clinical studies that evaluated the safety and efficacy of guselkumab in the treatment of adult participants with moderate-to-severe plaque psoriasis.

The null hypothesis of no dose-response relationship is to be tested at an overall Type 1 error rate of 0.05 (2-sided). Assuming a PASI 75 response rate of 6% and 80% in the placebo and JNJ-77242113 highest dose groups, respectively, a sample size of approximately 40 participants in the placebo group and each of the JNJ-77242113 treatment groups will provide an average power of at least 95% to detect a dose-response signal across different candidate dose-response models. [Table 1](#) and [Table 2](#) below show the candidate dose response models and the power to detect a dose-response signal based on the primary endpoint of the proportion of participants achieving PASI 75 at Week 16 for various candidate models.

Table 1: Candidate Dose-response^a Models

Model Type	Model specification ^b
E _{max} 1	dose/(35+dose) (ED ₅₀ =35)
E _{max} 2	dose/(50+dose) (ED ₅₀ =50)
Logistic	1/{1+exp[(35-dose)/15]} (ED ₅₀ =35, δ=15)
SigEMax	Dose ³ /((35) ³ +dose ³) (ED ₅₀ =35, h=3)
Linear	dose
Quadratic	dose-0.002*(dose**2) (δ=-0.002)

^a Response is PASI 75 response at Week 16.
^b A standardized version of the dose response model

Table 2: Summary of powers for each candidate models

Sample size Per Group	Emax 1	Emax 2	Logistic	SigEMax	Linear	Quadratic	Mean Power
40	>95%	>95%	>95%	>95%	>95%	>95%	>95%

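### Step 1 of the primary gMCP-Mod analysis carries no weight term, although allocation is balanced on weight and the pairwise CMH and MMRM analyses adjust for it: a small, nearly free gain in precision is left unused

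*SAP*

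**What the plan says.** - **Allocation.** Protocol 6.3 describes dynamic central randomization that limits imbalance within each "individual stratification factor: study site and baseline weight" (≤90, >90 kg).
- **Primary analysis.** SAP 5.3.1.2.3 extends MCP-Mod to a binary endpoint through "the use of an ANOVA style parameterization of the dose-response parameter", and for that step "a logistic regression of the event proportion at each dose level will be used". The estimates and their covariance, both on the logit scale, feed the contrast tests and the model fits. No covariate is named. By Protocol 9.4.2.1.1.1, this test alone decides whether the study is positive.
- **Pairwise tests of the same endpoint.** SAP 5.3.1.2.3.1 uses "The Cochran-Mantel-Haenszel chi-square statistic stratified by baseline weight category", with Mantel-Haenszel weights for the difference.
- **Other endpoints.** Secondary binary endpoints (SAP 5.4.1.3.1) follow the same CMH approach. The MMRMs (SAP 5.1 and 5.4.1.3.2) include weight category and its interaction with visit.
- **Estimand.** The population-level summary is a difference in proportions (SAP 5.3.1.2.1), and model estimates are displayed as proportions.

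**The concern.** When allocation is balanced on a factor that predicts response, the arms differ less by chance than under simple randomization. An analysis that ignores the factor still charges the full binomial variance, so its standard errors are too large and its test is conservative. Here that would fall on the one test that defines success and on the fitted curve that may support dose selection. The primary and pairwise results for PASI 75 at Week 16 would also rest on different adjustment bases.

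**Working it through.** **Inputs from the documents.** There are 40 participants in each of six arms. SAP 3.1 plans with "Assuming a PASI 75 response rate of 6% and 80% in the placebo and JNJ-77242113 highest dose groups"; Protocol 9.2 has 70% for the top dose. The critical value is set "at the overall one-sided alpha level of 0.025", which agrees with the two-sided 5% level. Contrasts, dose coding and the six candidate shapes come from SAP Tables 1 and 5.

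**Assumptions.** The documents give neither the effect of weight nor the share above 90 kg. For the variance I take two equal strata and one odds ratio common to all arms: 1.5, 2.25 or 3.45. At a 50% response rate these correspond to stratum differences of 10, 20 and 30 points.

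**The plan's own figures first.**
- With a covariance of 1/[40·p(1−p)] per arm and no weight term, the power of the dose-response test is above 99.9% for every candidate model at 6% vs 80%. The SAP's bound of more than 95% holds. At 6% vs 70% the mean is 99.995%, so the Protocol's 90% also holds.
- The same weight-free approach, taking p(1−p) from the linear model for all rows, reproduces Table 5 to 0.0001 in five rows and to 0.0009 in the logistic row. The planning contrasts thus came from an unadjusted step.

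**Overstatement in one arm.** With two equal strata that differ by D around a mean rate p, the excess share of the computed variance is

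r = 1 − mean[p_s(1−p_s)] / [p(1−p)] = (D/2)² / [p(1−p)].

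At odds ratio 2.25:
- p = 50%: strata 40% and 60%, so r = 0.10²/0.25 = 4.0%.
- p = 6%: strata 3.8% and 8.2%, so r = 0.0219²/0.0564 = 0.85%.
- p = 80%: strata 73.7% and 86.3%, so r = 0.0631²/0.16 = 2.5%.

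**Overstatement in a contrast.** On the logit scale, arm i contributes c_i²/[p_i(1−p_i)]. For the first Emax row of Table 5:
- Placebo: 0.6154²/0.0564 = 6.71.
- Top dose: 0.6731²/0.16 = 2.83.
- The four middle arms together: 0.77.
- Total: 10.31, so placebo carries 65%.

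At odds ratio 2.25 the weighted excess is (6.71×0.85% + 2.83×2.5% + 0.77×about 3.5%)/10.31 ≈ 1.5%.

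Over all six rows of Table 5:

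| Assumed odds ratio | Contrast variance overstated by | × 240 participants |
|---|---|---|
| 1.5 | 0.4–0.5% | about 1 |
| 2.25 | 1.5–2.1% | about 4–5 |
| 3.45 | 3.2–4.6% | about 8–11 |

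**Power and type I error.** These come from the joint normal distribution of the contrast statistics, with 200,000 draws. The unadjusted test was given its true variance under weight-balanced allocation. The adjusted step 1 had dose as a factor plus centred weight category. Odds ratios here are for >90 vs ≤90 kg, with half of participants above 90 kg.

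| Odds ratio | Mean power, 6% vs 30%: unadjusted → adjusted | One-sided type I error, unadjusted (flat response at 6–50%) |
|---|---|---|
| 0.67 | 86.8% → 86.9% | not run |
| 0.5 | 86.9% → 87.2% | 0.023–0.025 |
| 0.33 | 87.0% → 87.9% | 0.020–0.024 |
| 0.2 | 87.3% → 88.9% | 0.016–0.023 |

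The adjusted test holds 0.025 throughout. At the planned effects both versions exceed 99.9%. With rates standardized over the FAS in place of conditional logits, the gains at 6% vs 30% run from 0.1 to 1.5 points, so the picture is the same.

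**The case against.** **The decision does not depend on it.** Power is above 99.9% either way and the unadjusted test errs on the safe side. This stands, and it fixes the severity as minor.

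**The unadjusted model targets the estimand directly.** One parameter per dose gives marginal rates, whereas a covariate makes the logits conditional. This stands against simply adding a term. Standardizing the predictions answers it. If weight is exactly balanced across arms, the standardized rates equal the observed arm rates, and only the standard errors change.

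**Redaction may hide a covariate.** Blacked-out blocks stand in SAP 5.1 and 5.3.1.2.3, so this cannot be fully excluded. But the paragraph that defines step 1 is intact, and Protocol 9.4.1, which is not redacted, attaches weight to the CMH test and the MMRM and not to MCP-Mod. Table 5 is weaker evidence, because the contrasts are recalculated from the observed covariance.

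**Weight is examined elsewhere.** PASI 75 is also reported by weight over time (SAP 5.5.1.2.3) and in a subgroup (SAP 5.7.5). That is true, but neither changes the primary standard error.

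**Two stronger readings are tempting.**
- A reader might infer that the primary test is the only efficacy comparison without weight. It is not. Subgroup differences are explicitly unstratified (SAP 5.7.5), the Bayesian dose-response model has no weight term (SAP 5.3.1.2.4), and no stratification is stated for the Fisher's exact fallback (SAP 5.4.1.3.1). Study site is also a balancing factor, and neither the CMH tests nor the MMRMs adjust for it.
- A reader might take per-arm figures at response rates of 30–70% (about 1%, 4–5% and 9–11% for differences of 10, 20 and 30 points) and conclude that up to 22–26 of 240 participants are lost. The planned rates do not allow this. With two equal strata, a 6% placebo arm cannot have a difference above 12 points, and placebo carries 55–65% of the contrast variance in the Emax, logistic and sigmoid Emax rows.

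**Conclusion.** The point holds as a minor one. The visible primary analysis leaves out a balancing factor that the pairwise CMH and MMRM analyses include. If weight is prognostic, the primary standard errors are conservative: by 0.4–0.5% of the contrast variance at an odds ratio of 1.5, and by 3.2–4.6% at 3.45. If weight is not prognostic, nothing is lost. The sizes rest on an assumed common odds ratio, two equal strata, planned rates of 6% to 80%, and large-sample theory.

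The documents do not support a claim that the test is invalid, that type I error is inflated, or that the planned power is at risk.

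**What to change.** In SAP 5.3.1.2.3, specify step 1 as follows:
1. Fit a logistic regression with treatment group and weight category (≤90, >90 kg).
2. For each group, average the predicted response over all FAS participants to obtain a standardized rate.
3. Take logits of these rates with a delta-method covariance, and use them in the contrast tests, critical value and model fits, which otherwise stay as planned. The estimand remains a marginal proportion.

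Keep the unadjusted fit as a supportive analysis and as the named fallback if an arm has no responders. The fallback alone does not settle that case: at 6% and n = 40 the chance of no placebo responder is 0.94^40 = 8.4%, and the maximum-likelihood logit is then not estimable with or without weight. The SAP should say how such an arm is handled.

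If the sponsor prefers to leave step 1 unadjusted, one sentence giving the reason would be enough. The cost is SAP wording and a few lines of code, with no new data and no change to the sample size.
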